THE IRB MUST BE NOTIFIED OF COMPLETION OF THIS STUDY.....	32

REFERENCES	33
TABLES.....	34
TIMELINE AND EVENTS SCHEDULE.....	34
STUDY SCALES AND ASSESSMENTS.....	35

INVESTIGATOR'S STATEMENT OF AGREEMENT

I have read the foregoing protocol and agree that it contains all necessary details for conducting the study. I will conduct the study as outlined herein and will complete the study within the time designated.

I agree to conduct this protocol in accordance with local regulations, external standards and applicable ICH and Good Clinical Practice (GCP) guidelines.

I will provide copies of the protocol, including any amendments, and all pertinent information to all individuals responsible to me who assist in the conduct of this study. I will discuss this material with them to ensure they are fully informed regarding the ZELTIQ Aesthetics, Inc. device and the conduct of the study.

I further agree to provide access to ZELTIQ Aesthetics Inc, its designees, or regulatory authorities to any source documents from which case report form information may have been generated.

I agree to maintain the confidentiality of all information received or developed in connection with this protocol.

Principal Investigator
(Print name)

Principal Investigator
(Principal Investigator's signature)

Date

[figure not shown]
CLINICAL SITE

STUDY SYNOPSIS

Purpose	The purpose of this single-site clinical study is to evaluate the safety and effectiveness of three (3) treatments sessions with the ZELTIQ Aesthetics, Inc. Rapid Acoustic Pulse (RAP) device for the improvement in the appearance of cellulite.
Primary Effectiveness Objective	
 • RAP treatment effectiveness: The primary effectiveness objective will demonstrate improvement in the appearance of cellulite as determined by correct identification of baseline vs 12-weeks post final treatment images [REDACTED] [REDACTED] by at least 2 of 3 blinded independent physician reviewers (IPR).
Primary Safety Objective	
 • RAP treatment safety: The primary safety objective is to evaluate the safety of the RAP (Rapid Acoustic Pulse) device for cellulite treatments through the monitoring of the incidence of adverse events (AEs) and adverse device effects (ADEs); serious adverse events (SAEs) and SADEs (serious adverse device effects) and pain assessments.
Secondary Effectiveness Objective	
 • RAP treatment effectiveness: The secondary effectiveness objective is to demonstrate the improvement in the appearance of cellulite as determined by the study participants selecting “Agree” or “Strongly Agree” as answers to the Participant Satisfaction Survey (Assessment 3): when comparing side-by-side before and after photographs.
Test Device	ZELTIQ Aesthetics, Inc. Rapid Acoustic Pulse (RAP) device.
Treatment	
Each cellulite treatment session will consist of RAP treatment [REDACTED] to bilateral thigh and/or buttock areas using the same treatment settings for both sides.
 
The participants will have three (3) separate cellulite treatment sessions. The second treatment session will occur four (4) weeks post the initial treatment. The third treatment session will occur twelve (12) weeks post the second treatment.

Control	For each cellulite treatment area, the pre-treatment photos of the thighs and/or buttocks area will serve as a control.
Study Design	Non-significant risk, single-site, prospective clinical trial.
Planned Number of Sites / Countries	One clinical trial site located in the United States.

Planned Duration of Participant Engagement	Up to seventy-two (72) weeks [REDACTED]
Planned Number of Participants/ Treatment Areas	Up to 15 participants [REDACTED] (total of two thighs and/or buttocks per participant) The clinical site (CS) will recruit up to 15 participants. This will provide a total of up to thirty treatment areas.
Primary Effectiveness Endpoint	
 Effectiveness Endpoint: An Independent Photo Review (IPR) panel will be asked to identify the 12-weeks post final treatment photographs from randomly placed side-by-side before and after photographs, for all participants who meet all the inclusion criteria and none of the exclusion criteria and complete the 12-weeks follow-up visit. The number of before and after photos correctly identified by at least 2 of 3 blinded reviewers from the IPR panel will be recorded. [REDACTED]
Primary Safety Endpoint	
 RAP treatment safety endpoint: To demonstrate safety through the absence of unexpected adverse events (UAEs) and serious adverse events (SAEs) directly attributable to the RAP device or treatments.
Secondary Effectiveness Endpoint	
 Effectiveness Endpoint: For all participants who meet all inclusion criteria and none of the exclusion criteria and are followed up at the 12-week timepoint post final treatment, [REDACTED] he study participants select “Agree” or “Strongly Agree” to the Participant Satisfaction Survey (Assessment 3): [REDACTED]
[REDACTED]	

Inclusion Criteria	
 • Healthy candidates ages 18-50 years. • Seeking treatment of cellulite in the thigh and/or buttock areas. • Areas of moderate to severe cellulite on bilateral thigh and/or buttock using the Cellulite Dimple – At Rest Scale at Baseline with grades of 2 or 3 based on review of photos taken under the same lightening conditions planned for the trial. • Participant will not have had minimally invasive, invasive, or energy-based cellulite (liposuction, subcision, RF, laser, ESWT, cryo-lipolysis, muscle stimulation, etc.) treatments in the treatment areas in the prior 12 months. • Participant will not have used topical based cellulite treatments for prior 3 months and will not use during the trial. • Participant will not have used spray-on tanning treatments for 3 months prior to or during the term of the trial. • Participant must be able to provide written informed consent, understand and is willing to comply with all study-related procedures and follow-up visits.
Exclusion Criteria	
 • Participant is unwilling to have research photos and/or videos taken of treatment areas in the presence of or by Sponsor's research team. • Participant is unwilling to have RAP treatment provided in the presence of Sponsor's research team. • Participant is pregnant or planning to become pregnant during the duration of the study. • Participant is unwilling to commit to follow-up visits.

	
 • Metal or plastic implants (vascular stent, or implants in the hips, knees, etc.) in the treatment areas. • Active electronic implants such as pacemakers and defibrillators. • History of coagulopathy and/or on anticoagulant medication. • Skin disorders (skin infections or rashes, psoriasis, etc.) in the treatment areas. • Medical disorder that would hinder wound healing or immune response. • Any surgical procedure in the treatment areas in the prior 3 months or planned during the duration of the study. • Any other condition/disease/situation which, as deemed by the PI, would preclude participant from safely participating in or completing the study visits or that may confound study results.
--	---

INTRODUCTION

Overview

The Rapid Acoustic Pulse (RAP) is an electrohydraulic (EH) device designed to improve the appearance of cellulite. Devices using RAP technology have been successfully used in seven human clinical trials to accelerate laser-based tattoo removal, a proof of concept (POC) and pivotal clinical trials to improve the appearance of cellulite without the occurrence of device related UAEs or SAEs. The purpose of this single-site, multi-treatment clinical study is to evaluate the safety and effectiveness of ZELTIQ Aesthetics, Inc.’s Rapid Acoustic Pulse (RAP) device for the improvement of cellulite.

Cellulite

Cellulite is the often aesthetically displeasing rippling or dimpling of the skin most commonly located on the thighs and buttocks of women. Its appearance and texture are often likened by laypeople to that of “cottage cheese” or an orange peel [1].

In a paper discussing anatomical approaches to treating cellulite by Christman et al [1], “In normal skin, there is a support network of fibrous septa running through the subcutis, separating the adipose cells into chambers resembling a quilt. Magnetic resonance imaging demonstrates that in cellulite, these fibrous septa are contracted and sclerosed, ultimately tethering the skin at a fixed length. Concurrently, the adipose cells expand with weight gain or water absorption, promoting herniation, or outpouching of fat into the dermis. This results in skin dimpling creating the characteristic cellulite appearance. Two distinct morphologies of cellulite may be identified, sometimes coexisting in the same patient: 1) diffuse rippling in patients with increased adiposity and/or increased skin laxity and 2) dimpling, with discrete ellipsoid or linear depressions, in patients with good skin tone [1].”

Christman concluded, "It is crucial to consider the anatomy of the patient and the morphology of cellulite while choosing a treatment. Diffuse rippling represents increased adiposity and/or increased skin laxity which may stand to benefit from lipolytic and skin tightening modalities. Dimpling represents tethering by fibrous septa which may stand to improve from subcision by minimally invasive devices such as Cellfina [1]."

ZELTIQ Aesthetics, Inc.'s Rapid Acoustic Pulse (RAP) device with Cellulite Cartridge

ZELTIQ Aesthetics, Inc.'s Rapid Acoustic Pulse (RAP) technology was developed to improve the appearance of cellulite through microscopic disruption of the fibrous septa leading to an improvement in the appearance of cellulite dimples and ridges.

RAP comprises multiple components, including the console, handpiece, and the cable connecting the handpiece to the console. The disposable electrohydraulic cartridge is an electro-mechanical device that converts an electrical signal into mechanical (acoustical) energy. The RAP device produces [REDACTED] planar acoustic waves at a pulse rate of [REDACTED]. This high pulse rate causes non-invasive fibrous structure disruption without cavitation damage or thermal degradation of the surrounding tissue that are seen with focused acoustic devices.

Physical Effects

RAP can induce physical effects in the form of disruption (i.e., subcision) of the fibrous structures that make up the extracellular matrix or in the case of subcutaneous tissue, the fibrous septa. These physical effects appear to be through shearing of the fibrous structures.

The high frequency wavefront's [REDACTED] play a critical role in shear-induced tissue injury. The greater the gradient, the more fibrotic disruption occurs [2]. Importantly, while shock-induced shearing might initiate disruption, individual high frequency acoustic waves do not produce sufficient shear to do so [3].

To produce enough fibrotic disruption from shearing, multiple acoustic shock waves need to be administered to the treatment site. For example, in a paper by Howard [4] of the mechanical effects of focused shock waves on tissue-mimicking structures, membrane disruption is observed to increase progressively as the number of shock waves increases. For example, kidney injury from shock waves during lithotripsy pervade the focal region of the kidney parenchyma after 1000 or 2000 shock waves [4].

However, it is not just the number of shock waves that are important to affect tissue. If you provide one thousand shock waves to a kidney over a period of hours or days, there will be little if any tissue damage. [REDACTED]

[REDACTED]

[REDACTED]

The RAP improves the appearance of cellulite through disruption of the subcutaneous fibrous septa leading to a reduction in the severity of dimples and ridges.

Proof of Concept (POC) of Safety and Tolerability of RAP Cellulite Clinical Trial

In the proof-of-concept cellulite clinical trial that was initiated in June 2018 at SkinCare Physicians, the primary objectives of that study were to assess the safety and tolerability of the RAP treatment, and the secondary objective was to determine if the RAP treatment could provide improvement in appearance of cellulite.

Both thighs in five participants (10 treatment areas) having Grade II cellulite, were treated with the RAP device with [REDACTED] pulse rate. On one site, a single RAP treatment was provided. On the other site, a RAP treatment was given every three weeks for a total of three RAP treatments. Immediately after each RAP treatment, the treated areas were assessed for AEs. Additionally, the participants were asked about discomfort from the procedure. Finally, photographs of the treatment areas taken prior to, and at 12-weeks post the first treatment, were assessed to determine if the RAP treatment had the effect of improvement in the appearance of cellulite.

Results indicated there were no safety or discomfort issues resulting from the RAP treatments. Mild redness around hair follicles, which resolved within hours was the only side effect. There were no reports of erythema, swelling or bruising. [REDACTED]

Safety Conclusion

[figure not shown]
Given the safety and tolerability results of the Acoustic Wave Device (AWD) in the POC cellulite human clinical trial, the RAP device is anticipated to be safe and tolerable when used in this clinical trial. The RAP device that will be used in this study uses the same Rapid Acoustic Pulse technology that is the basis for ZELTIQ Aesthetics, Inc.'s AWD (Acoustic Wave Device) and RAP devices in earlier trials.

Pivotal Study of Safety and Efficacy of RAP Cellulite Clinical Trial

A multi-center, pivotal study was conducted to assess the safety and efficacy of the ZELTIQ Aesthetics, Inc. RAP device for the temporary improvement of cellulite on the treatment areas of thighs and/or buttocks. Sixty-seven participants enrolled in the study. Treatments were conducted at [REDACTED] Efficacy was documented at 12- weeks post treatment. No SAE or device related unexpected or SAE occurred during the study.

Short-term (12-week) analysis was conducted in fifty-six participants who completed a full treatment of the identified treatment areas and who completed the 12-week follow up visit. Serial clinical photographs were collected before RAP treatment under standardized conditions at the baseline (0-week) visit and at the short-term (12-week) follow-up visits. Photographs were assessed by blinded independent reviewers (IPR) to correctly identify the 12-weeks post-treatment photographs from randomly placed side-by-side comparison of before and after photographs. Additionally, the IPR graded the pre-treatment and post-treatment images using the simplified 6-point Cellulite Severity Scale (CSS) [3] and improvement using the Global Aesthetic Improvement Scale (GAIS). Safety assessments included evaluation of Adverse Events (AEs) via physician examination during and after the treatment.

[figure not shown]
The short-term (12-week) results demonstrated that a single non-invasive acoustic subcision session can safely provide meaningful improvement in the appearance of cellulite in terms of depressions with minimal treatment pain and no post-treatment down time. The post-treatment photographs were correctly identified by blinded IPR from randomized pairs of pre/post-treatment photographs at a rate of 96.4%. Furthermore, the participants had a mean CSS reduction of 1.01 (a 29.5% reduction from baseline). Cellulite was graded as improved, much improved, or very much improved using the GAIS at 90.9% of treated locations. Finally, 92.9% of participants reported positive satisfaction responses. No device related unexpected or serious AEs were noted at treatment or follow-up. Overall average pain score during treatment was 2.4 (0-10 pain scale) and 0.3 immediately post-treatment.

[figure not shown]

Protocol 2021-06 Study Objectives and Endpoints

Primary Objectives	Primary Outcome Endpoints
RAP treatment effectiveness: The primary objective is to demonstrate improvement in the appearance of cellulite by blinded independent physician reviewers (IPR).	Effectiveness Endpoint: An IPR panel will be asked to identify the 12-weeks post final treatment photographs from randomly placed side-by-side before and after photographs, for all participants who meet the all inclusion criteria and none of the

	
exclusion criteria and complete the 12-week follow-up visit. The number of before and after photos correctly identified by at least 2 of 3 blinded reviewers from the IPR panel will be recorded.
 
[REDACTED]

RAP treatment safety: The primary objective is to evaluate the safety of the RAP device for cellulite treatments.
	
RAP treatment safety endpoint: The numbers and proportions of participants with AEs, SAEs, ADEs, SADEs, and unanticipated AEs or ADEs will be summarized.
 
RAP treatment safety: The safety objective is to evaluate the safety of the RAP (Rapid Acoustic Pulse) device for cellulite treatments through the monitoring of the incidence of adverse events (AEs) and adverse device effects (ADEs); serious adverse events (SAEs) and SADEs (serious adverse device effects) and pain assessments.

Secondary Objectives	Secondary Outcome Endpoints

RAP treatment effectiveness: The secondary objective is to demonstrate the improvement in the appearance of cellulite as determined by the study participants.
	
For all participants who meet all inclusion criteria and none of the exclusion criteria and are followed up at the 12-week timepoint post final treatment,
 
[REDACTED]
 
[REDACTED]
 
In comparison to the pre-treatment photo, the 12-week photograph of the treatment area appears improved.

STUDY DESIGN

This is a non-significant risk, single-center, prospective trial for safety, and effectiveness using ZELTIQ Aesthetics, Inc.'s RAP device for the improvement in the appearance of cellulite performed at 1 clinical research site in the United States.

Up to fifteen (15) healthy participants between the age of 18-50 will be enrolled in this study.

Participants who sign the informed consent form and meet all the eligibility criteria will be enrolled in the study. Each participant will undergo acoustic rapid pulse (RAP) treatments on both of their thighs and/or buttocks.

Total study duration is anticipated to be at or less than 72 weeks from the first participant visit to the last participant observation visit. A total of up to 7 visits are planned for this study [REDACTED].

Selection of Study Population

The clinical study can fulfill its objectives only if appropriate participants are enrolled.

The following criteria are designed to select participants for whom protocol requirements are considered appropriate.

Participants who meet all inclusion criteria and none of the exclusion criteria will be enrolled in the study and assigned a participant No./ID in sequential order (i.e., 01, 02, 03, etc.)

[figure not shown]
Inclusion Criteria

- Healthy candidates ages 18-50 years
- Seeking treatment of cellulite in the thigh and/or buttock areas
- Areas of moderate to severe cellulite on bilateral thigh and/or buttock using the Cellulite Dimple – At Rest Scale at Baseline with grades of 2 or 3 based on review of photos taken under the same lightening conditions planned for the trial.
- Participant will not have had minimally invasive, invasive or energy-based cellulite (liposuction, subcision, RF, laser, ESWT, cryo-lipolysis, muscle stimulation, etc.) treatments in the treatment areas in the prior 12 months.
- Participant will not have used topical based cellulite treatments for prior 3 months and will not use during the trial.
- Participant will not have used spray-on tanning treatments for 3 months prior to or during the term of the trial.
- Participant must be able to provide written informed consent, understand and is willing to comply with all study-related procedures and follow-up visits.

Exclusion Criteria

- Participant is unwilling to have research photos and/or videos taken of treatment areas in the presence of Sponsor's research team.
- Participant is unwilling to have RAP treatment provided in the presence of Sponsor's research team.
- Participant is pregnant or planning to become pregnant during the duration of the study.
- Participant is unwilling to commit to follow-up visits.

- Metal or plastic implants (vascular stent, or implants in the hips, knees, etc.) in the treatment areas.
- Active electronic implants such as pacemakers or defibrillators.
- History of coagulopathy and/or on anticoagulant medication.
- Skin disorders (skin infections or rashes, psoriasis, etc.) in the treatment areas.
- Medical disorder that would hinder wound healing or immune response
- Any surgical procedure in the treatment areas in the prior 3 months or planned during the duration of the study.
- Any other condition/disease/situation which, as deemed by the PI, would preclude participant from safely participating in or completing the study visits or that may confound study results.

STUDY PROCEDURES

Study procedures as described in this section are outlined in the schedule of assessments.

Study Visits

Visit 1 Baseline Screening and Consent Form (Day -30 to Day 0)

- Review study procedures, assessments and visit schedule with participants
- [REDACTED]
- Obtain informed consent
- Review of Inclusion/Exclusion criteria
- [REDACTED]
- Fitzpatrick Skin Type Scale (Scale 2)
- [REDACTED]
- Demographics and baseline characteristics (including weight and height)
- Limited physical exam, blood pressure and heart rate
- Review of medical history (3-year history)
- Urine pregnancy test for women of childbearing potential
- Concomitant medication
- 2D Photos of the treatment area
- [REDACTED]

Visit 2 Treatment

Pre-treatment Activities

- Review concomitant medication
- Take vital signs
- Urine pregnancy test for women of childbearing potential
- Adverse event evaluation
- Confirm eligibility
- [REDACTED]
- 2D Photos of the treatment area taken pre and post marking
- [REDACTED]

Note: Visits 1 and 2 may be combined if feasible at time of screening and enrollment.

Treatment

- Administer treatment in accordance with Treatment Recommendations (**See Appendix A, Treatment Recommendations**)

Immediate Post-Treatment Activities

- Adverse event evaluation

Visit 3 Follow Up Visit 4-Weeks Post 1st Treatment (+/- 14 days) and 2nd Treatment

Pre-treatment Activities

- Review concomitant medication
- Take vital signs
- Weight
- Urine pregnancy test for women of childbearing potential
- Adverse event evaluation
- Confirm eligibility
- Collect Diary – Treatment 1
- [REDACTED]
- 2D Photos of the treatment area taken pre and post marking

Treatment

- Administer treatment [REDACTED]

Immediate Post-Treatment Activities

- Adverse event evaluation [REDACTED]

Visit 4 Follow Up Visit 12-Weeks Post 2nd Treatment (+/- 14 days) and 3rd Treatment

- Review concomitant medication
- Take vital signs
- Weight
- Urine pregnancy test for women of childbearing potential
- Adverse event evaluation
- Confirm eligibility
- [REDACTED]
- [REDACTED]
- 2D Photos of the treatment area taken pre and post marking [REDACTED]

Treatment

[figure not shown]
- Administer treatment in accordance with Treatment Recommendations (See Appendix A, Treatment Recommendations)

Immediate Post-Treatment Activities

[figure not shown]
- Adverse event evaluation [REDACTED]

Visit 5 Follow Up Visit 12- Weeks Post 3rd Treatment (+/- 14 days)

[figure not shown]
- Weight
- Review concomitant medication
- Adverse Event evaluation
- [REDACTED]
- 2D Photos of the treatment area

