The investigational site will provide direct access to all trial-related site's source data/documents, and reports for the purpose of monitoring and auditing by ZELTIQ Aesthetics, Inc. or designee, and inspection by local and regulatory authorities (as appropriate).

The investigational site will have established standard operating procedures (SOPs) for quality management. Data will be evaluated for compliance with the protocol and accuracy in relation to source documents. The study will be conducted in accordance with procedures identified in the protocol.

The data and any research conducted will be controlled by ZELTIQ Aesthetics, Inc.

STUDY RESULTS/ANALYSIS

Sample Size Determination: Up to fifteen (15) participants will be enrolled and treated in this study. The sample size is based on clinical and practical exploratory considerations and not a formal statistical power.

Demographics and Baseline Characteristics: Demographic and baseline characteristics will include age, sex, ethnicity, race, gender identity, height, and weight, Fitzpatrick Skin Type, and Cellulite Dimple assessment of bilateral posterior thighs and/or buttocks.

Study Analysis Populations: The Full Analysis Set (FAS) will include all participants who meet all the inclusion and none of the exclusion criteria, received assigned three treatments with the device and completed the 12-week, follow-up visits per the protocol. The FAS will be treated as the primary analysis set.

Effectiveness Parameter Analysis: Descriptive statistics will be performed on the population per protocol, all participants completing the study without major protocol deviations. Descriptive statistics (i.e., mean, standard deviation, etc.) will be provided for all continuous variables, percentages and frequencies for all categorical variables collected in this study.

Summary tables will be used to present population characteristics at Baseline. For categorical parameters, the number and percentage of participants in each category will be presented. The denominator for percentage will be based on the number of participants appropriate for the purpose of analysis. For continuous parameters, descriptive statistics will include n (number of participants), mean, standard deviation, median, and range. No imputation will be used to account for missing data. No processing for outliers will be performed. Data will be presented as reported on the CRF. [REDACTED]

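### The primary endpoint counts correct identification of the post-treatment photograph as cellulite improvement, so lucky guesses and any non-cellulite cue enter the count

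*Combined protocol and SAP*

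**What the plan says.** In the Study Synopsis, the primary effectiveness objective is to "demonstrate improvement in the appearance of cellulite as determined by correct identification of baseline vs 12-weeks post final treatment images". The primary effectiveness endpoint in the same table gives the task: the panel "will be asked to identify the 12-weeks post final treatment photographs from randomly placed side-by-side before and after photographs". The scoring rule, given there and again in the table of Study Objectives and Endpoints, is: "The number of before and after photos correctly identified by at least 2 of 3 blinded reviewers from the IPR panel will be recorded".

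The visible text does not ask which photograph shows less cellulite, does not offer a no-difference answer, and does not compare the count with what guessing would give. The control is the participant's own pre-treatment photograph.

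On size, "Up to fifteen (15) participants will be enrolled and treated in this study", and the Synopsis adds: "This will provide a total of up to thirty treatment areas". Study Results/Analysis plans descriptive statistics and says: "The sample size is based on clinical and practical exploratory considerations and not a formal statistical power".

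Text is redacted within the objective and directly after the endpoint.

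**The concern.** The objective concerns how the cellulite looks. The task concerns which picture came second. The two agree when cellulite improvement is the only thing that tells the pictures apart, and can differ otherwise. A reviewer who sees no change but must choose is right half the time. A reviewer who uses some other consistent difference between the two occasions is right more often than that. An area that has visibly changed without improving could also be scored correct. All of these enter the count that the objective calls improvement.

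The visible plan has no untreated pairs that would show how often reviewers succeed without a treatment effect. A reader given a bare percentage is likely to take it as the share of participants or areas improved, and that share could be considerably lower.

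**Working it through.** The plan states no success rate, power or error rate in its visible text, so there is no figure to reproduce. The checks below ask what an identification percentage would mean.

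**Inputs from the documents.** Two photographs per pair in random position; three reviewers; a pair counts when at least 2 are right; up to 15 participants or 30 areas.

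**Assumptions.** The choice is forced. Truly improved pairs are always recognised. The reader accuracies in step 3 are illustrative; the documents give none.

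**1. Majority rule under guessing.** If each of three independent readers is right with probability p, at least 2 are right with probability p²(3 − 2p). At p = 0.5 this is 0.25 × 2 = 0.50. If all three always agree, it is also 0.50. The 2-of-3 rule therefore gives no protection against guessing: 7.5 of 15 pairs, or 15 of 30, would be expected correct with no visible change in any of them.

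**2. From identification to improvement.** If a share q of pairs is truly improved and the rest are guessed, the expected rate is q + (1 − q) × 0.5.
- q = 0.4: 0.4 + 0.3 = 0.70
- q = 0.6: 0.6 + 0.2 = 0.80

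So 70% correct corresponds to about 40% improved, and 80% to about 60%.

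**3. A consistent non-cellulite cue with no improvement at all.** The result depends on how readers' errors are related.

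| Reader accuracy (assumed) | Errors fully shared | Errors independent |
|---|---|---|
| 0.6 | 60% | 0.36 × 1.8 = 64.8% |
| 0.7 | 70% | 0.49 × 1.6 = 78.4% |
| 0.8 | 80% | 0.64 × 1.4 = 89.6% |

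At 0.7 this is 15 × 0.70 = 10.5 to 15 × 0.784 = 11.8 of 15 pairs. A cue that sits in the photograph acts on all three readers together, which points towards the shared column; the independent column is the upper end.

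**4. What a comparison with 50% would settle.** With 15 pairs, 12 correct (80%) is the smallest count with a one-sided exact probability under guessing below 0.025 (0.0176; 11 correct gives 0.059). That would rule out guessing throughout. By step 2, it would still be compatible with about 60% improved.

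**5. The same rule with a no-difference option.** If three options are guessed equally, each reader picks the post-treatment image with probability 1/3, and the 2-of-3 rule credits (1/9) × (7/3) = 7/27 = 25.9% of unchanged pairs. By symmetry the same share is expected for the pre-treatment image. If readers never use the third option, the figure returns to 50%.

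**The case against.** Much of the case on the other side stands.

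- **Redaction.** The blacked-out text may hold a success threshold or a blinded grading, and the reviewer form is not shown. A threshold would deal with guessing at group level, but it would not remove guessed pairs from the count or separate cellulite from other cues. A grading would help, although the visible primary objective would still rest on identification.
- **Safeguards.** Reviewers are blinded and placement is random. Spray tanning and topical cellulite products are barred, and the inclusion criteria refer to lighting planned for the trial. The Photography section, however, promises standardised conditions for baseline images only. Treatment-visit images are taken before and after skin marking, and the visible text does not say which serves as the before image.
- **Direction of a cue.** Hair or natural tan can tell two pictures apart without showing which came later. A cue raises the rate only if it runs consistently in one direction, and the documents show no such cue.
- **The pivotal study.** The Introduction reports 96.4% identification beside 90.9% of locations graded improved on GAIS. The formula in step 2 turns 96.4% into 2 × 0.964 − 1 = 92.8%. The units may differ and gaps are small at high rates, so this is only indicative. It gives no ground for saying that identification misled there.
- **The secondary endpoint** asks about improvement directly, but of participants, who are not blinded.

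Three stronger readings are tempting and not supported. A reader might infer that the 2-of-3 rule amplifies a cue that the reviewers share; amplification needs independent errors, and a fully shared cue stays at its own strength. A reader might infer that lingering bruising gives the pictures away; the proof-of-concept study reported no bruising, and only mild redness that cleared within hours. A reader might infer that worsened areas will be scored as successes; this is possible, but a reviewer may well pick the better-looking image as the later one, and nothing in the documents shows otherwise.

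**Conclusion.** The point holds as a mismatch between the stated objective and the visible task. If the choice is forced, half of the unchanged pairs are credited, and 70% or 80% correct would mean about 40% or 60% improved. A consistent non-cellulite cue could raise the rate further, to between 60% and 90% over the accuracies assumed, even with no improvement. These figures rest on the forced choice, on sure recognition of improved pairs, and on accuracies that are not taken from the documents.

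The documents do not show that such a cue exists or that the eventual result will be inflated. With up to 15 participants, a descriptive analysis and no formal power, the effect is on how the percentage may be read and not on an error rate. The change is worth making because it costs little and ties the count to the objective.

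**What to change.** Keep the three blinded reviewers and the randomly placed pairs, and settle the following before reading starts.

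1. Ask first, before any identification question: *Which photograph shows less visible cellulite: left, right, or no difference?* The order matters, because naming the post-treatment image first could steer the answer on cellulite.
2. Count a pair as improved only when at least 2 of 3 choose the post-treatment image, and base the improvement statement on this count.
3. Report beside it the pairs in which at least 2 of 3 choose the pre-treatment image. This is the chance reference, since equal guessing among three options would still credit 26% of unchanged pairs.
4. Then ask the identification question. Report its rate against the 50% guessing rate and for comparison with the pivotal study's 96.4%.

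The cost is an added question on the reviewer form and a change to the endpoint wording, with no extra readers or images. The improvement rate will probably be lower than the identification rate and is not directly comparable with 96.4%. Real change in cellulite from other causes, such as weight, remains uncontrolled, as it is in the present design.
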